4.1 Inclusion Criteria

Subjects aged 18 to 70 will be **eligible for inclusion** in this study if all the following criteria apply:

1. Willing to provide written informed consent
2. Have symptoms of urinary incontinence for at least 3 consecutive months
3. For male subjects: If subject has undergone any prostate procedure, this must have occurred at least 6 months prior to screening
4. Have at least 7 incontinence episodes per week in the diary entries for the Screening Placebo Run-In Period
5. Subject is ambulatory and able to use the toilet independently
6. If subjects use pelvic floor exercises, subjects must have been on a stable exercise and activity regime for at least 3 months prior to screening and that regime must remain stable during the treatment period
7. Subject has a body mass index (BMI) $\geq 19 \text{ kg/m}^2$ but $\leq 35 \text{ kg/m}^2$ (BMI=weight [kg] / height [m^2])
8. Subjects must have a pre-dose mean systolic/diastolic blood pressure of $\leq 140/90 \text{ mmHg}$ before randomization can occur
9. For female subjects: Must not be pregnant, lactating, or actively trying to become pregnant. Subjects who are premenopausal and of childbearing potential must have a negative pregnancy test at Screening (serum) and at Day 0 (urine) and must use a medically acceptable and effective method of birth control for the duration of the study, which can include:
 - a. Having a male partner who is sterile prior to the female subject's entry into the study and is the sole sexual partner for that female subject
 - b. Use of double-barrier methods of contraception; condoms with the use of caps (with spermicide) and intra-uterine devices are acceptable
 - c. Use of hormonal contraceptives (oral, depots, patches, etc.) with double-barrier methods of contraception as outlined above

- d. True abstinence: When this is in line with the preferred and usual lifestyle of the subject (period abstinence [eg, calendar, ovulation, symptothermal, post-ovulation methods] and withdrawal are not acceptable methods of contraception)
- 10. Subjects taking oral contraceptives or hormone replacement therapy (women) or hormone adjuvant therapy (men) must have a stable dose and regimen for ≥ 3 months prior to entry into the study

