6.2 Efficacy Parameters

6.2.1 *Bladder Diary Questions*

The bladder diary will be completed daily for the 7 days prior to visit 2 and visit 6, to record the number of incontinence episodes and whether these were nocturia events. If a subject has multiple events in 1 day, each event will preferably be entered separately. The number of incontinence pads used will also be recorded in the diary.

Subjects will be instructed on how to use the bladder diary and complete the assessments.

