5.4 Efficacy Variables

Bladder Diary Questions

The bladder diary will be completed daily for the 7 days prior to visit 2 and visit 6, to record the number of incontinence episodes and whether these were nocturia events. If a subject has multiple events in 1 day, each event will preferably be entered separately. The number of incontinence pads used will also be recorded in the diary.

Percentage change in number of incontinence episodes in a week

The number of incontinence episodes entered into the eCRF is the total number of events a subject recorded during the 7day period prior to visit 2 and visit 6. This number will be directly used in the calculation of % change in number of incontinence episodes in a week

Number of Incontinence Episodes/24 hours (daily average)

The number of incontinence episodes entered in the eCRF will be divided by 7 to compute the number of episodes/24 hours (daily average). This consideration follows the assumption that the bladder diary will be filled by the subject for the 7 days prior to Visit 2 and Visit 6 and that the patient entered all episodes occurred in this period. Therefore, the following formula will be used:

$$\text{Number of Incontinence episodes / 24 hours} = \frac{\text{Number of incontinence episodes recorded}}{7}$$

Number of Nocturia Episodes in a week

The number of nocturia episodes entered in the eCRF is the total number of nocturia episodes a subject recorded during the 7day period prior to Visit 2 and Visit 6. The value entered in the eCRF will be used in the efficacy analysis of nocturia episodes without any adjustment.

Number of Incontinence Pads per week

The number of incontinence pads entered in the diary represents the number of pads used in a week, therefore the value entered in the eCRF will be used in the analysis without any adjustment.

This consideration follows the assumption that the bladder diary is completed by the subject for the 7 days prior to Visit 2 and Visit 6 and that the patient entered all pads used in this period.

Proportion of subjects who become continent

A subject is defined as continent if he/she has no incontinence episodes.

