6.9 Efficacy Analyses

Efficacy will be assessed by the number of urinary incontinence episodes. There is only one hypothesis so there will be no adjustment for multiplicity.

The efficacy analysis will be performed on the ITT and PP populations.

There will not be an adjustment for multiple comparisons for these efficacy analyses.

Baseline for all efficacy endpoints will be defined as the last week of the Screening Placebo Run-In Period (Visit 2). The final measurement (endpoint) will be defined as Week 8 (Visit 6).

1. Percentage change from end of the Screening Placebo Run-In Period to Week 8 in the number of incontinence episodes in a week

The efficacy analysis planned is an analysis of covariance model (ANCOVA). Percentage change in the number incontinence episodes/week is the response variable. The factor variables will be dose and centre. If the center effect is significant, summary statistics will be presented to describe the effect. The covariate will be end of the Screening Placebo Run-In Period episodes of incontinence.

The percentage change, $\%UIE_i$, for subjects in each arm, is expressed as the ratio of the total number of urinary incontinence episodes in a week between final measurement ($UIE_{i,end}$) and baseline ($UIE_{i,base}$)

$$\%UIE_i = \frac{UIE_{i,end}}{UIE_{i,base}}$$

Since percentage change from baseline does not have the properties of additivity and symmetry, it will be log-transformed, and the response variable will be the natural logarithm of the ratio of Week 8 (Visit 6) to Baseline, as shown below:

$$\log(\%UIE_i) = \log\left(\frac{UIE_{i,end}}{UIE_{i,base}}\right)$$

The hypothesis test being conducted is as follows:

$$\begin{aligned} H_0: \log(\%UIE_{\text{Litoxetine}}) - \log(\%UIE_{\text{Placebo}}) &= 0 \\ H_1: \log(\%UIE_{\text{Litoxetine}}) - \log(\%UIE_{\text{Placebo}}) &\neq 0, \end{aligned}$$

This is equivalent to testing the hypothesis:

$$H_0: \log\left(\frac{\%UIE_{Litoxetine}}{\%UIE_{Placebo}}\right) = 0$$

The result of the ANCOVA model will be expressed as log % and then back transformed to percentage change. Therefore, H_0 can be interpreted as:

$$H_0: \frac{\%UIE_{Litoxetine}}{\%UIE_{Placebo}} = 1$$

This makes the actual statistics:

$$\delta = \log(\%UIE_{Litoxetine}) - \log(\%UIE_{Placebo}) = \log\left(\frac{\%UIE_{Litoxetine}}{\%UIE_{Placebo}}\right)$$

When back-transformed, this is expressed as follows:

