$$\Delta = \exp\left(\log\left(\frac{\%UIE_{Litoxetine}}{\%UIE_{Placebo}}\right)\right) = \frac{\%UIE_{Litoxetine}}{\%UIE_{Placebo}}$$

$\%UIE_i$ is the ratio of the total number of urinary incontinence episodes in a week at endpoint (Visit 6) ($UIE_{i,end}$) to the total number of urinary incontinence episodes in a week at baseline ($UIE_{i,base}$) for arm i , with i equal to Litoxetine or Placebo.

An ANCOVA will be performed to compare δ to 0; the test will provide an appropriate p-value with a significance level alpha equal to 0.05. This p-value will be computing the probability of observing a difference among arms.

Numbers of incontinence episodes equal to 0 (not missing) will be imputed as 0.4 to allow for the log transformation.

2. Absolute change from end of the Screening Placebo Run-In Period to Week 8 in the number of incontinence episodes/24 hours (daily average)

The analysis planned is an analysis of covariance model (ANCOVA). Absolute change in the total number of incontinence episodes/24 hours is the response variable. The factor variables will be dose and centre. The covariate will be end of the Screening Placebo Run-In Period episodes of incontinence.

Number of incontinence episodes/24 hours will be computed as Total Number of incontinence episodes recorded during the 7-day period and entered in the eCRF divided by 7, as defined in Section 5.4.

The hypothesis test being conducted is as follows:

$$H_0: \Delta UIE_{Litoxetine} - \Delta UIE_{Placebo} = 0$$
$$H_1: \Delta UIE_{Litoxetine} - \Delta UIE_{Placebo} \neq 0$$

Where ΔUIE_i is the absolute change, for subjects in arm i , in the number of incontinence episodes/24 hours as defined above from baseline ($UIE_{i,base}$) to the final measurement ($UIE_{i,end}$):

$$\Delta UIE_i = UIE_{i,end} - UIE_{i,base}.$$

Where i goes from 1 to 2 and it represents the 2 arms: Litoxetine and Placebo.

3. Proportion of subjects who become continent at Week 8

A subject is defined as continent if s/he has no incontinence episodes at Visit 6 (Week 8). Frequencies will be used to describe the proportion of subjects who are continent at Week 8. The proportion will be computed on the total number of subjects for each arm at baseline. The category Missing will be included in the analysis, to consider subjects who do not attend the visit or who have missing values for that visit.

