Differences between groups will be evaluated using Chi-square test or Fisher's exact test (if more than 20% of the cells in a contingency table have counts less than 5).

4. Change from end of the Screening Placebo Run-In Period to Week 8 in the number of incontinence pads used per week

The analysis planned is an analysis of covariance model (ANCOVA). Absolute change in the number of incontinence pads used per week is the response variable. The factor variables will be dose and centre. The covariate will be the number of pads used at the end of the Screening Placebo Run-In Period.

Number of incontinence pads used per week will be derived for the eCRF, as defined in Section 5.4.

The hypothesis test being conducted is as follows:

$$\begin{aligned} H_0: \Delta \text{Pads}_{\text{Litoxetin}} - \Delta \text{Pads}_{\text{Placebo}} &= 0 \\ H_1: \Delta \text{Pads}_{\text{Litoxetin}} - \Delta \text{Pads}_{\text{Placebo}} &\neq 0 \end{aligned}$$

Where ΔPads_i is the absolute change, for subjects in arm i , in the number of incontinence pads used per week from baseline ($\text{Pads}_{i,\text{base}}$) to the final measurement ($\text{Pads}_{i,\text{end}}$):

$$\Delta \text{Pads}_i = \text{Pads}_{i,\text{end}} - \text{Pads}_{i,\text{base}}.$$

Where i goes from 1 to 2 and it represents the 2 arms: Litoxetin and Placebo.

5. Percentage change from end of the Screening Placebo Run-In Period to Week 8 in the number of nocturia episodes in a week

The analysis planned is an analysis of covariance model (ANCOVA). Percentage change in the total number of nocturia episodes in a week is the response variable. The factor variables will be dose and centre. The covariate will be end of the Screening Placebo Run-In Period episodes of incontinence.

The number of nocturia episodes in a week is the total number of nocturia episodes recorded over the 7-day period and entered in the eCRF, as defined in Section 5.4.

The analysis will be carried out as described in section 6.9 point 1.

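### The nocturia analysis borrows a log ratio with zeros set to 0.4 for a count that may be zero at baseline or Week 8, and adjusts for the wrong baseline

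*SAP*

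**What the plan says.** The nocturia endpoint was added in the SAP (1.5 item a) and is the fifth secondary endpoint (2.4 item 5). In SAP 6.9 point 5, "Percentage change in the total number of nocturia episodes in a week is the response variable", the factors are dose and centre, and "The covariate will be end of the Screening Placebo Run-In Period episodes of incontinence". For the method, "The analysis will be carried out as described in section 6.9 point 1".

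Point 1 was written for total incontinence episodes. There, "the response variable will be the natural logarithm of the ratio of Week 8 (Visit 6) to Baseline", and "Numbers of incontinence episodes equal to 0 (not missing) will be imputed as 0.4 to allow for the log transformation".

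The only entry criterion on diary counts, Protocol 4.1 item 4, is "Have at least 7 incontinence episodes per week in the diary entries for the Screening Placebo Run-In Period". It does not distinguish night from day.

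Protocol 6.2.1 and SAP 5.4 describe the diary in the same terms: it is kept "to record the number of incontinence episodes and whether these were nocturia events". SAP 5.4 adds that "The value entered in the eCRF will be used in the efficacy analysis of nocturia episodes without any adjustment". Neither document defines nocturia.

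**The concern.** A log ratio is workable for total episodes because the entry criterion keeps the baseline at 7 or more per week. The nocturia count, as described, is a subset of those episodes. A subject with seven daytime leaks and none at night is eligible, with a nocturia baseline of 0. Small baselines also make a Week 8 count of 0 likely.

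Three consequences follow.

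- The score for any subject with a zero at either visit is set by the constant 0.4. The SAP gives no reason for that value, and its wording refers only to incontinence episodes.
- The between-arm ratio is compressed if Week 8 zeros are common, so a real reduction would be understated.
- The covariate is the baseline of a different variable, so the model does not adjust directly for the subject's own starting level.

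At stake is whether a reported nocturia result, tested at two-sided 0.05, describes the drug's effect or the choice of constant.

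**Working it through.** The plan states no nocturia mean, zero fraction, effect size or power, so there is no figure of its own to reproduce.

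**Step 1: scores under the 0.4 rule.** Score = ln(Week 8 / baseline), with 0 replaced by 0.4 (SAP 6.9 point 1).

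| Change | Ratio | Log |
|---|---|---|
| 0 to 0 | 0.4/0.4 = 1.00 | 0 |
| 0 to 1 | 1/0.4 = 2.50 | +0.916 |
| 0 to 3 | 3/0.4 = 7.50 | +2.015 |
| 1 to 0 | 0.4/1 = 0.40 | -0.916 |
| 7 to 8 | 8/7 = 1.14 | +0.134 |
| 10 to 7 | 7/10 = 0.70 | -0.357 |

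One new episode from zero carries 0.916/0.357 = 2.6 times the log weight of a fall of three episodes from ten. The weight depends on the constant: 0 to 1 is a ratio of 10 with 0.1, 4 with 0.25, 2.5 with 0.4, 2 with 0.5 and 1 with 1.

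**Step 2: effect on the between-arm ratio.** Everything here is assumed: gamma-Poisson weekly counts with mean m and shape k, Week 8 mean 0.6m on drug and m on placebo, so the true ratio is 0.60. The probability of a zero is (k/(k+mean))^k. For m = 1 and k = 1 this is 1/2 at baseline and 1/1.6 = 0.625 at Week 8 on drug. The last column is the back-transformed difference in mean log ratio.

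| Mean per week | Shape | Zero at baseline | Zero at Week 8, drug | Estimated ratio |
|---|---|---|---|---|
| 1 | 1 | 50% | 63% | 0.78 |
| 1 | 3 | 42% | 58% | 0.76 |
| 2 | 1 | 33% | 45% | 0.71 |
| 2 | 3 | 22% | 36% | 0.66 |
| 3 | 1 | 25% | 36% | 0.67 |
| 3 | 3 | 13% | 24% | 0.62 |
| 7 | 1 | 13% | 19% | 0.62 |
| 7 | 3 | 3% | 7% | 0.58 |

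With m = 1 and k = 1, the same data give 0.66 with a constant of 0.1, 0.78 with 0.4 and 0.88 with 1.

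**Step 3: which zeros cause the shrinkage.** Randomisation gives both arms the same baseline distribution, so mean ln(baseline) cancels from the treatment difference. Comparing mean ln(Week 8) alone gives, for the first six rows, 0.784, 0.761, 0.706, 0.664, 0.668 and 0.618. These match the table within simulation error. The shrinkage therefore comes from Week 8 zeros, and the substituted baseline adds variance. Restricting to a baseline of at least 1 still returns 0.71 to 0.73 at a mean of 1.

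**Step 4: the alternative.** SAP 6.9 point 4 analyses pads as absolute change, with dose and centre as factors and baseline pads as covariate. The plan's 60 evaluable subjects at 2:1 give 40 and 20. In simulations of that size without a centre effect, the same form of model for nocturia returned the true mean difference (-0.4m) to within simulation error. Power at means of 1 to 3 rose from 0.19-0.45 under the planned model to 0.30-0.65. Part of that gain comes from using the variable's own baseline: against a log-ratio model that already does so, it was 0.01 to 0.15.

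**The case against.** The strongest reply is that the plan is computable and little depends on it. Point 5 adopts point 1 as a whole, including its zero rule, so a reader who infers that the ratio is undefined at a zero baseline goes too far. That rule is worded for incontinence episodes, which calls for a clarification. Nocturia is the fifth secondary endpoint in a trial whose primary objective is safety and whose efficacy aim is exploratory. No sample size or decision rule rests on it. All of this stands and limits the importance of the point.

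Other stronger readings also fail.

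- A reader might infer that zero baselines bias the estimate. Step 3 shows that they do not; Week 8 zeros do.
- A reader might infer that subjects with zero at baseline cannot show benefit. That is true of a within-subject fall, but a zero in one diary week is not a zero underlying rate. In the assumed model, such subjects on drug end 0.2 to 0.6 episodes per week below their placebo counterparts.
- A reader might conclude that the variable is certainly mislabelled. The diary text reads as a flag on leaks, but the diary form is not in the documents and the term is undefined.

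Choosing absolute change over a ratio is partly preference. Absolute change has the same floor for a subject who starts at zero. The reply does not justify the arbitrary constant or the mismatched covariate.

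**Conclusion.** The point holds as a moderate one. Point 5 carries a log ratio with a 0.4 substitution over to a count with no guaranteed minimum, so part of the result is set by the constant. It also adjusts for baseline incontinence, although Protocol 8.8.2 asks for a baseline suited to each further endpoint and point 4 does this for pads.

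The algebra in step 1 is certain if the 0.4 rule applies. The size of the distortion is not: the estimates of 0.62 to 0.78 against a true 0.60 rest on assumed means of 1 to 3 per week. A reader might infer from the top of that range that nearly half the effect is lost, but this is only the lowest assumed mean. At a mean of 7 the estimate is 0.58 to 0.62, and the documents do not show which setting applies.

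**What to change.** - **Endpoint and model (SAP 2.4 item 5 and 6.9 point 5).** Replace percentage change with absolute change in nocturia episodes per week, analysed by ANCOVA with dose and centre as factors and baseline nocturia episodes as covariate, following point 4. Keep subjects with zero at baseline in the analysis.
- **Ratios.** Present any ratio or percentage as descriptive only, with the number of zero baselines in each arm.
- **Name.** Report the variable as nocturnal incontinence episodes per week, unless the diary form shows that night-time voids without leakage are also recorded. State the definition in SAP 5.4.

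The cost is SAP wording only. The data are the same and the model form is already specified for pads. There are two downsides: the estimate is in episodes per week and not in percent, and absolute change still has a floor for subjects with zero at baseline.

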6.9.1 Sensitivity Efficacy Analyses

For the Efficacy Analyses relating to the number of incontinence episodes, a sensitivity analysis without imputation will be performed.

The sensitivity analyses will be performed on the ITT only, since the imputation method is not used in the PP population.

As with the Efficacy Analysis, baseline for all sensitivity endpoints will be defined as the last week of the Screening Placebo Run-In Period. The final measurement (endpoint) will be defined as Week 8 (Visit 6).

A second set of sensitivity analysis compares the placebo group with the patients in the litoxetine arm at 30 mg who did not have a dose reduction.

A third set of tables will analyse the absolute change of the number of incontinence episodes in a week and the percentage change in the number of incontinence episodes/24 hours.

1. Percentage change from end of the Screening Placebo Run-In Period to Week 8 (Visit 6) in the number of incontinence episodes in a week (without imputation)

This sensitivity analysis will use an ANCOVA model. It will follow the efficacy analysis described in section 6.9 point 1.

The imputation method will not be applied.

2. Change from end of the Screening Placebo Run-In Period to Week 8 (Visit 6) in the number of incontinence episodes/24 hours (daily average) (without imputation)

The change in the total number of incontinence episodes in a week will be analysed with an ANCOVA model. It will follow the efficacy analysis described in section 6.9 point 2.

The imputation method will not be applied.

3. Percentage change from end of the Screening Placebo Run-In Period to Week 8 (Visit 6) in the number of incontinence episodes in a week for patients without a dose reduction

The percentage change in the total number of incontinence episodes in a week will be analysed with an ANCOVA model. It will follow the efficacy analysis described in section 6.9 point 1. In the litoxetine group, only patients who did not have a dose reduction will be considered. Therefore, subjects who are dispensed the 30 mg dose at visit 5 will be considered in the litoxetine group.

4. Change from end of the Screening Placebo Run-In Period to Week 8 (Visit 6) in the number of incontinence episodes/24 hours (daily average) for patients without a dose reduction

The change in the total number of incontinence episodes/24 hours will be analysed with an ANCOVA model. It will follow the efficacy analysis described in section 6.9 point 2. In the litoxetine group, only patients who did not have a dose reduction will be considered. Therefore, subjects who took the 30 mg dose at visit 6 will be considered in the litoxetine group.

5. Percentage change from end of the Screening Placebo Run-In Period to Week 8 (Visit 6) in the number of incontinence episodes/24 hours (daily average)

This exploratory analysis will use an ANCOVA model. It will follow the efficacy analysis described in section 6.9 point 1.

The number of incontinence episodes/24 hours (daily average) will be used as endpoint.

6. Change from end of the Screening Placebo Run-In Period to Week 8 (Visit 6) in the number of incontinence episodes in a week

The change in incontinence episodes in a week will be analysed with an ANCOVA model. It will follow the efficacy analysis described in section 6.9 point 2.

The total number of incontinence episodes in a week will be used as endpoint.

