3 OVERALL DESIGN AND PLAN OF THE STUDY

3.1 Overview

This is a Phase 1/2a, double-blind, randomised, placebo-controlled, parallel-group study in subjects 18 to 70 years old diagnosed with UI.

The study will include a 2-week, single-blind (subject blind) Screening Placebo Run-In Period and an 8-week double-blind Treatment Period. The Treatment Period will be followed by a 1-week Dose-tapering Period. Subjects will return to the clinic for a safety Follow-up Visit 4 weeks after treatment is completed for a total study duration of 15 weeks. No interim analysis is planned.

All subjects will enter the Screening Placebo Run-In Period during which eligibility will be assessed and placebo run in medication will be provided. During this period, 7 days daily diary symptoms will be collected. Subjects who continue to meet eligibility criteria after the Screening Placebo Run-In period, including collection of diary data will enter the Treatment Period and be randomly assigned (2:1) to receive study drug (litoxetine 10 mg, 20 mg, 30mg, or placebo) BID.

[figure not shown]
Litoxetine treatment will be provided with dose titration, starting with 10 mg BID for 1 week, escalated to 20 mg BID for 1 week, and subsequently escalated to 30 mg BID for 6 weeks' duration (for a total litoxetine treatment period of 8 weeks). Placebo treatment will be matched.

If the subject does not tolerate the last dose level escalation (ie cannot tolerate 30 mg BID), the dose can be reduced to the previous dose level (20 mg BID). If the patient does not tolerate the lower dose level (20 mg BID) s/he will be discontinued from the study. After 8 weeks of treatment, doses will be reduced by 50% over 1 week to taper off treatment. A safety follow up visit will occur 4 weeks after treatment is permanently stopped (total study duration 15 weeks)

Safety assessments will be conducted throughout the trial and will include physical examinations, vital signs, evaluation of psychiatric status (suicidality, depression symptoms, anxiety and sleep related symptoms), clinical laboratory evaluations, 12-lead electrocardiograms (ECGs), and adverse events (AEs).

Efficacy will be assessed by number of urinary incontinence episodes and the number of incontinence pads used.

A schedule of assessments is provided in [Appendix 2](#). A schematic of the study design is presented in [Figure 1](#).

Figure 1: Study Design

BID = twice daily

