4.1 Study Populations

The study population will consist of subjects with UI. Subjects must be able to provide written consent and meet all the inclusion criteria and none of the exclusion criteria.

A valid efficacy measurement is defined as a valid number of incontinence episodes as recorded in the bladder diary and uploaded in the eCRF at Visit 2 and Visit 6, i.e. either as 0 or greater than 0.

There are 4 analysis populations for this study:

Randomised population:

Defined as all subjects randomised to treatment (Visit 2).

Safety population:

Defined as all subjects who are randomised to treatment (Visit 2), receive study drug, and undergo at least 1 visit.

Intent-to-Treat (ITT) population:

Defined as all subjects who are randomized to treatment (Visit 2), receive at least one dose of study drug and have a valid efficacy measurement at Baseline (Visit 2).

Per Protocol (PP) population:

Defined as those subjects who are randomised, receive at least one dose of study drug, provide a valid efficacy measurement at Baseline (Visit 2) and a valid end of study primary efficacy endpoint (Visit 6), and have completed the study without a major protocol deviation.

The following populations are defined for analysis purposes:

1. Enrolled Population: each subject that signed the Informed Consent form and entered the Screening Period.
2. Completers Population: each subject that completed the trial, per protocol.
3. Full Analysis Set Population: each subject which is in either ITT or PP population.

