6.3 General Methodology

Safety

Safety data will be presented and analysed using the Safety Population.

The primary safety analyses include all treatment emergent adverse events defined as any AE started after Visit 2. The analysis will be carried out with point estimates and Clopper Pearson 95% confidence intervals.

Descriptive statistics will be provided for all variables in the summary tables by treatment group according to the type of variable summarised.

Quantitative variables will be summarised by using n (number of subjects per group), arithmetic mean, standard deviation (SD), median and range (minimum and maximum).

Categorical variables will be summarised by using frequency distributions and percentages.

The number of Adverse Events and the number and the percentage of patients experiencing those events, will be summarised by treatment group. Differences between groups will be evaluated using Chi-square test or Fisher's exact test. Subgroup analysis of differences between groups of AEs will be performed separately for patients who had an adverse event while on the 10mg dose (AE started from Visit 2 and Visit 3), 20 mg dose (AE started from Visit 3 and Visit 4) and 30 mg dose (AE started from Visit 4 and Visit 6). Subjects with adverse events who deviated from the protocol dosage will be highlighted in the footnotes.

Shift tables will be used to describe the evaluation of clinical significance for laboratory values, 12-Lead ECG and physical examination.

For all analyses, hypothesis testing will be carried out at the alpha = 0.05 level (two-sided) when comparing treatments. P-values will be rounded to three decimal places. Statistical significance will be declared if the rounded p-value will be less than or equal to 0.05.

Efficacy

For the PP efficacy analysis of incontinence episodes, only valid efficacy endpoints at Visit 6 will be used. For the ITT efficacy analysis of incontinence episodes, valid and imputed endpoints at Visit 6 will be used. The imputation method is described in section 6.1. No LOCF from baseline will be used for any efficacy analysis.

Descriptive statistics will be provided for all variables in the summary tables by treatment group according to the type of variable summarised.

Quantitative variables will be summarised by using n (number of subjects per group), arithmetic mean, standard deviation (SD), median and range (minimum and maximum).

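### The no-dose-reduction sensitivity analysis selects on tolerability in the litoxetine arm only, and its two points define the selected group differently

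*SAP*

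**What the plan says.** SAP 5.4.1 and 6.9.1 describe a second set of sensitivity analyses that "compares the placebo group with the patients in the litoxetine arm at 30 mg who did not have a dose reduction". Point 3 covers percentage change in weekly episodes and point 4 covers absolute change in episodes per 24 hours. Both carry the restriction "In the litoxetine group, only patients who did not have a dose reduction will be considered", and neither restricts the placebo group.

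Each point then turns the restriction into a rule:

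- Point 3: "Therefore, subjects who are dispensed the 30 mg dose at visit 5 will be considered in the litoxetine group".
- Point 4: "Therefore, subjects who took the 30 mg dose at visit 6 will be considered in the litoxetine group".

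On the population, 6.9.1 says "The sensitivity analyses will be performed on the ITT only". SAP 4.1 opens its ITT definition with "Defined as all subjects who are randomized to treatment (Visit 2), receive at least one dose of study drug" and adds a valid baseline measurement; it sets no condition on tolerability or completion. SAP 6.3 adds "For the ITT efficacy analysis of incontinence episodes, valid and imputed endpoints at Visit 6 will be used". Within 6.9.1, only points 1 and 2 switch imputation off.

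Protocol 3.1 says of the titration "Placebo treatment will be matched". SAP section 3 applies the titration steps to both treatments, and both documents write the reduction rule for any subject who cannot tolerate 30 mg BID, not for one arm.

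**The concern.** There are two separate problems.

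First, the filter is one-sided. Keeping the 30 mg dose is decided after randomisation and reflects how well a subject tolerates treatment. Litoxetine subjects who fail the condition are removed, and so are those who left before Visit 5. Placebo subjects with a blinded reduction stay, as do placebo subjects who left early, with imputed Visit 6 values. The comparison is then between litoxetine tolerators and unselected placebo subjects. If tolerability goes with outcome, part of any difference reflects selection, and the analysis cannot serve as a robustness check on the randomised comparison.

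Second, the two points give different operational meanings to the same condition. Point 3 fixes membership at Day 35, point 4 at Day 70. The percentage and absolute results may then rest on different litoxetine subjects, and two programmers could build different analysis sets from the same text.

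**Working it through.** The documents give no sample size, power or error rate for this analysis, so there is no stated figure to reproduce. The check sets the rules side by side and then illustrates the possible size.

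**1. Who is kept**

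| Subject | Litoxetine | Placebo |
|---|---|---|
| Reduced from the 30 mg level by Visit 5 | removed | kept |
| Left before Visit 5 | removed | kept, Visit 6 imputed if missing |
| Reduced or lost between Visits 5 and 6 | can be kept in point 3, not in point 4 | kept |
| On 30 mg level to Visit 6 | kept | kept |

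The imputation entry assumes that 6.3 governs points 3 and 4, since neither point says otherwise.

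**2. Timing of the two rules**

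From the schedule of assessments, 30 mg starts at Visit 4 (Day 28), Visit 5 is Day 35 and Visit 6 is Day 70.

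- Planned time at 30 mg: 70 − 28 = 42 days.
- Elapsed when the point 3 rule is set: 35 − 28 = 7 days.
- Not covered by the point 3 rule: 70 − 35 = 35 days, and 35/42 = 83%.

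The variables are also unclear. Protocol 7.1.5 lists dispensing at Visit 5, but the dispensing row of the schedule (Protocol Appendix 2 and SAP Figure 1) has no mark there. At Visit 6 the drug dispensed is the taper supply (Protocol 7.1.6).

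**3. Possible size of the selection effect**

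Assume no drug effect, a normal outcome, and a latent intolerance score with correlation r to a worse outcome. Exclude the fraction p with the highest scores from litoxetine only. In SD units, in favour of litoxetine:

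bias = r × φ(z) / (1 − p), where z is the (1 − p) quantile of the standard normal.

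| p (assumed) | r (assumed) | φ(z) | φ(z)/(1 − p) | bias (SD) |
|---|---|---|---|---|
| 0.15 | 0.2 | 0.2332 | 0.274 | 0.055 |
| 0.25 | 0.3 | 0.3178 | 0.424 | 0.127 |
| 0.35 | 0.4 | 0.3704 | 0.570 | 0.228 |

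Unrounded, the low end is 0.0549. At r = 0 the bias is zero; if r is negative the sign reverses.

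**4. Effect on the test**

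The planned 78 subjects at 2:1 give 52 and 26. A null simulation (20,000 runs per scenario, two-sided t-test at 0.05, litoxetine-only filter, no covariates and no imputation) gave these rejection rates:

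| Excluded | r = 0 | r = 0.3 | r = 0.5 |
|---|---|---|---|
| 10% | 4.9% | 5.9% | 7.1% |
| 20% | 4.8% | 7.0% | 11.2% |
| 30% | 5.0% | 9.2% | 17.1% |
| 40% | 5.1% | 11.1% | 23.5% |

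The corresponding bias is 0.06 to 0.19 SD at r = 0.3 and 0.10 to 0.32 SD at r = 0.5. With an assumed SD of 0.8 for the log ratio, the spurious litoxetine/placebo ratio runs from 0.96 to 0.77 over the scenarios with r above 0.

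With the same filter in both arms and the same intolerance process in both, bias stayed within 0.003 SD of zero and rejection rates were 4.8 to 5.2%.

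**The case against.** The case against is substantial. This is a labelled sensitivity analysis of a secondary endpoint in a trial whose primary objective is safety. The SAP states the comparison openly and rests no conclusion on it. Comparing subjects held at the target dose with all placebo subjects is a recognisable exposure question, and a placebo reduction changes no active exposure. All of that stands, and it limits the weight of the point. It does not explain why placebo dropouts stay while equivalent litoxetine dropouts go.

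A reader might infer that the filter must produce a spurious difference favouring litoxetine. The documents do not support that. They give no reduction rate and no link between tolerability and outcome; with no link, the simulation shows no distortion.

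A reader might also infer that points 3 and 4 necessarily analyse different subjects. That is not shown either. Both share the same governing restriction, and read strictly under it a late-reduced subject would leave both. No clinic visit is scheduled between Visits 5 and 6, only a telephone contact on Day 42, so supply given at Visit 5 may be what is taken up to Visit 6. The sets can still diverge through dropout or an unscheduled reduction, and nothing in the SAP says which sentence prevails.

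Finally, filtering both arms does not restore randomisation. An active drug may have a different intolerance pattern from placebo, so the symmetric version reduces the problem without guaranteeing its removal. This is why the label belongs in the fix.

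**Conclusion.** The point holds in a limited form. On the text, the filter applies to one arm although titration and reduction apply to both, and one condition is implemented in two unreconciled ways. The first can bias the comparison if tolerability is related to outcome: about 0.05 to 0.23 SD under the assumed 15 to 35% exclusion and correlation of 0.2 to 0.4, nothing at zero correlation, and the opposite sign if poor tolerators do better. The second means the two endpoints may rest on different litoxetine subjects.

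Neither problem reaches the main ITT or PP analyses. The consequence is that points 3 and 4, as written, cannot be read as support for the robustness of the randomised result.

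**What to change.** Amend SAP 5.4.1 and 6.9.1 before unblinding.

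1. Use one rule for points 3 and 4: the subject reached the 30 mg level, or its matching placebo level, at Visit 4 and was still on it, with no recorded reduction, up to Visit 6. The 30 mg condition has to stay. A rule based only on the absence of a recorded reduction would retain subjects who left in week 1 without reaching that level.
2. Apply the rule identically to litoxetine and placebo.
3. State how dropouts before Visit 6 are handled, including whether imputed values are used, and do the same in both arms.
4. Label the result a non-randomised supportive comparison, because a symmetric filter removes the bias only if the intolerance process is similar in both arms.
5. Reconcile the Visit 5 dispensing entry between Protocol 7.1.5 and the schedule of assessments, so that the variable behind the rule is defined.

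The cost is a few sentences of SAP text and probably a few placebo subjects leaving a supportive analysis. SAP 6.4 already plans to tabulate dose reductions and the dose taken at each visit, so no new data should be needed. The change concerns the analysis set only, not dosing or clinical management.
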